#### 2. OBJECTIVES AND DESIGN

## 2.1 Study Objectives

## 2.1.1 Primary Objective

The primary objective of this study is to investigate the efficacy of 50 mg opicapone when administered with the existing treatment of L-DOPA plus a DDCI, in Parkinson's disease (PD) patients with end-of dose motor fluctuations and associated pain.

#### 2.1.2 Secondary Objectives

The secondary objectives of this study are:

- to investigate the efficacy of opicapone 50 mg in reducing further symptoms
- to investigate the safety and tolerability of opicapone 50 mg once daily

#### 2.2 Study Endpoints

#### 2.2.1 Primary Efficacy Endpoints

The primary efficacy endpoint of this study is change from baseline in Domain 3 (fluctuation-related pain) of King's Parkinson's Disease Pain Scale (KPPS).

#### 2.2.2 Secondary Efficacy Endpoints

The secondary efficacy endpoints of this study are:

- change from baseline in Domain B (anxiety) of Movement Disorder Society-sponsored Nonmotor Rating Scale (MDS-NMS)
- change from baseline in Domain A (depression) of MDS-NMS
- change from baseline in Domain K (sleep and wakefulness) of MDS-NMS
- change from baseline in total score of MDS-NMS
- change from baseline in Domain 4 (nocturnal pain) of KPPS
- change from baseline in total score of KPPS
- change from baseline in Movement Disorder Society-sponsored Unified Parkinson's Disease Rating Scale (MDS-UPDRS) Part III and IV
- change from baseline in Parkinson's Disease Questionnaire (PDQ-8)
- Clinical Global Impression of Change (CGIC)
- Patient's Global Impression of Change (PGIC)
- change from baseline in functional status via Hauser's PD diary
- changes from baseline in morning dystonia
- frequency of use of rescue medication

## 2.2.3 Safety Endpoints

The safety endpoints of this study are:

- incidence of adverse events (AEs) including serious adverse events (SAEs); relatedness to opicapone and severity will also be evaluated
- changes from baseline in vital signs
- changes from baseline in physical and neurological examinations
- changes from baseline in routine laboratory parameters

I-DM-011SAP Page 10 of 49

#### 2.3 Overall Study Design

This is a randomised, double-blind, placebo-controlled, multi-centre, parallel group, interventional clinical study in PD patients with end-of-dose motor fluctuations and associated pain. The study consists of a 1-week screening period, a 24-weeks double-blind treatment period and 2 weeks of follow-up period.

At Visit 1, the patient will complete initiation procedures. Moreover, the patient will be provided with a paper-based self-rating diary (Hauser's PD diary) and will be instructed how to complete it.

Completion of Hauser's PD diary entries will be reviewed at Visit 2a. In case the patient completed the diary satisfactorily the investigator will immediately continue with Visit 2b at the same day. If diary entries are non-compliant (i.e. more than 3 missing entries per day in the 3 days prior to Visit 2a), the patient will be re-trained on the correct use of the diary and Visit 2b will be postponed for 3 to 4 days.

At Visit 2b (Day 1) and if eligibility is confirmed, the patient will be randomised to 50 mg opicapone or placebo once daily (1:1) and start treatment in addition to current treatment with L-DOPA/DDCI.

Opicapone enhances the effects of L-DOPA. Hence, it may be necessary to reduce the patient's L-DOPA/DDCI dose within the first days or weeks of opicapone treatment. If dose decrease of L-DOPA/DDCI is deemed necessary, it may be adjusted by phone at Visit 3 or an unscheduled on-site visit may be performed at the investigator's discretion. The dosage of L-DOPA/DDCI should not be changed from Visit 4 through the end of the study.

No new anti-PD drugs should be started during the study and any that are ongoing at the start of the study must be kept at a stable dose throughout the study, unless for safety reasons. No new pain medication should be started during the study except the allowed rescue medication.

Patients who discontinue study participation prematurely will be asked to come to the site for an early discontinuation visit (EDV) as soon as possible (not exceeding 7 days after early discontinuation).

#### 2.4 Randomisation

Randomisation will follow a 1:1 allocation rate for each of the treatment arms (50 mg opicapone or placebo). No stratification factors were considered for randomisation.

At Visit 1, each patient will be assigned in a chronological order via electronic case report form (eCRF) to a patient unique number within the study. The patient number will be transferred by the site staff to the interactive web response system (IWRS). At Visit 2b, after confirming that the patient is eligible for entry into the treatment phase, the site staff will contact the IWRS in order to get the appropriate medication number from the system.

Patient recruitment will be competitive. It is possible for clinical study sites with a high recruitment rate to enrol more patients. Other clinical study sites could be slow at enrolling.

## 2.5 Treatments

Each patient will continue with his/her current daily L-DOPA/DDCI dose (3 to 8 daily doses) and will additionally take one capsule of IP (opicapone 50 mg as test product of this study or matching placebo) once daily for the duration of 24 weeks, starting in the evening of Visit 2b.

**Table 1: IP Description** 

Name of IP	Opicapone	Placebo
Dosage form	Hard capsule	Hard capsule
Active ingredient	Opicapone (BIA 9-1067), (2,5-dichloro-3-[5-{3,4-dihydroxy-5-nitrophenyl}-1,2,4-oxadiazol-3-yl]-4,6-dimethylpyridine 1-oxide)	Not applicable
Strength/concentration	50 mg	Not applicable

The last IP intake will take place in the evening prior to Visit 6. The IP should be taken once daily at bedtime, at least 1 hour before or after the last daily dose of L-DOPA/DDCI. The patients will be instructed to swallow the capsule whole with a glass of water.

I-DM-011SAP Page 11 of 49

In case one dose of IP is missed, the next dose should be taken as scheduled. The patient should not take a double dose to make up for the missed dose.

Patients are allowed to use rescue medication provided by sponsor:

- paracetamol (500 mg tablets; 4 g (3 g for German sites) per day at maximum) (unless patient already receives tramadol)
- tramadol (50 mg capsules; 400 mg per day at maximum).

Concomitant use of both types of rescue medication during the same day is not allowed. In case the patient needs to switch to tramadol, an unscheduled visit for dispensation of tramadol may be performed as required.

## 2.6 Sample Size

For the primary endpoint (change from baseline in Domain 3 of KPPS), a difference to placebo of 3.0 is regarded as clinically meaningful and from a former study (Rascol O et al 2016; DOI: 10.1002/jcph.678) a standard deviation of 5.8 can be assumed in both arm groups. With a two-sided significance level  $\alpha$  of 0.05, a power of 80%, a 1:1 treatment allocation ratio and with the abovementioned assumptions,  $2 \times 60 = 120$  evaluable patients are required. An approximate drop-out rate of 15% is assumed, therefore 140 patients need to be randomised.

**Post-BDRM note**: 144 patients were screened and 127 were randomised. Sample size differs from planned because study was early terminated. As the drop-out rate was less than 15%, the early termination will not have an impact. A total of 120 evaluable patients were required and 122 subjects belong to the full analysis set.

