At V2b (Day 1) and if eligibility is confirmed, the patient will be randomised to 50 mg opicapone or placebo once daily (1:1) and start treatment in addition to current treatment with L-dopa/DDCI.

Opicapone enhances the effects of L-dopa. Hence, it may be necessary to reduce the patient's L-dopa/DDCI dose within the first days or weeks of opicapone treatment. Therefore, the investigator will call the patient on Day  $8\pm 2$  (V3) to ask for any changes in the medical condition. If dose decrease of L-dopa/DDCI is deemed necessary, it may be adjusted by phone at V3 or an unscheduled on-site visit may be performed at the investigator's discretion. In case of L-dopa/DDCI adjustment an unscheduled phone call should be repeated up to 7 days after dose adjustment or V4 (Day  $29\pm 2$ ) should be performed, whatever applies first. The investigator can decrease the daily dose of L-dopa/DDCI (but keeping the number of daily intakes unchanged) as required until V4. If the investigator finds that the dose reduction was

too much, it can be increased again up to the baseline dose level. The dosage of L-dopa/DDCI should not be changed from V4 through the end of the study. No new anti-PD drugs should be started during the study and any that are ongoing at the start of the study must be kept at a stable dose throughout the study. No new pain medication should be started during the study except the allowed rescue medication. Baseline dose of pain medication may be reduced throughout the study if required due to pain medication-related AEs. If the investigator finds that the dose reduction was too much, it can be increased again up to the baseline dose level.

Further visits will be performed on Day  $85 \pm 4$  (V5, after 12 weeks) and Day  $169 \pm 4$  (V6, after 24 weeks). The primary analysis will be performed on the data collected at V6. A follow-up Visit (FU) will be performed on Day  $183 \pm 4$ , approximately 2 weeks after last intake of the investigational product (IP; 50 mg opicapone or placebo).

Patients who discontinue study participation prematurely will be asked to come to the site for an early discontinuation visit (EDV).

At V6 (or EDV, if applicable) the investigator will arrange for the patient's subsequent treatment, i.e. either prescribe further opicapone or switch to another treatment.

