#### **Statistical methods:**

The analyses of all efficacy endpoints will be based on the full analysis set (primary analysis population) and per-protocol set for sensitivity purpose.

The primary efficacy endpoint (change from baseline to V6 in the Domain 3 of KPPS) will be analysed using Analysis of Covariance (ANCOVA) with treatment as fixed factor and baseline KPPS as a covariate to demonstrate superiority of opicapone against placebo.

The key secondary endpoint (change from baseline in Domain B [anxiety] of MDS-NMS) as well as all other secondary efficacy endpoints will be analysed in an exploratory manner by treatment arm using appropriate parametric or non-parametric statistical methods. Descriptive statistics including 95%-confidence intervals will be presented per treatment arm. Potential sensitivity analyses will be specified in the *statistical analysis plan* (*SAP*).

The analyses of all safety endpoints will be based on the safety set.

All AEs will be summarised by number and percent of patients with AEs. Treatment-emergent AEs (TEAEs) will be summarised by calculating the number and percent of patients with AEs by preferred term (PT) and system organ class (SOC). TEAEs will also be summarised by severity and relationship to treatment. Number and percent of patients with serious TEAEs,

related serious TEAEs and TEAEs leading to discontinuation from study will be provided by SOC and PT. All AEs, SAEs and TEAEs leading to study termination will be listed.

Vital signs and laboratory parameters will be summarised by calculating summary statistics on the absolute values and on the change from baseline. Abnormal values will be assessed as clinically significant or not clinically significant.

Summary statistics and shift tables will be performed for physical examinations and, neurological examinations. Abnormal values will be assessed as clinically significant or not clinically significant.

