# Sample size:

For the primary endpoint (change from baseline in Domain 3 of KPPS), a difference to placebo of 3.0 is regarded as clinically meaningful and from a former study (Rascol O et al 2016; DOI: 10.1002/jcph.678) a standard deviation (SD) of 5.8 can be assumed. With a two-sided significance level  $\alpha$  of 0.05, a power of 80%, a 1:1 treatment allocation ratio and with the abovementioned assumptions, 2 x 60 = 120 evaluable patients are required. A drop-out rate of 15% is assumed, therefore 140 patients need to be randomised.

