#### 3. ANALYSIS SETS AND SUBGROUPS

#### 3.1 Analysis Sets

The **Enrolled Set** will be defined as all patients who signed informed consent.

The **Randomised Set** will be defined as all randomised patients.

The **Safety Set (SS)** will be defined as all patients randomised who took at least one dose of IP. Subjects will be analysed according to actual treatment taken.

The Full Analysis Set (FAS) will be defined as all patients who were randomised and who had at least one post-baseline assessment of primary efficacy measurement. Subjects will be analysed according to randomised treatment.

The **Per-Protocol Set (PPS)** will be defined as all patients who were included into the FAS and had no major protocol deviations that could have an influence on the primary efficacy endpoint. Subjects will be analysed according to randomised treatment. Patients that will belong to or will be excluded from the PPS will be discussed case-by-case by reviewing protocol deviations during Blind Data Review (BDR) meeting.

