## **Use of EDVs Data**

Data collected at EDV will be used for efficacy analysis, only if EDV assessments were performed no later than 3 days after last IP intake. The EDV which follows the rule will be assigned to the closest scheduled post-baseline analysis visit by target day (same visit windows as in Table 4). If the EDV is assigned to already performed scheduled visit, then non-missing assessment which is closest to the target day will be selected for the analysis. Other visits will be used according to analysis time windows as in Table 4..

This rule will be used for the total scores and subscores of KPPS, MDS-NMS, MDS-UPDRS and PDQ-8 analysis, as well as for the Clinical Global Impression of Change (CGIC), Patient's Global Impression of Change (PGIC) and morning dystonia.

EDV data will be assigned to the closest scheduled post-baseline analysis visit by target day if period analysis is needed for change of L-DOPA, rescue diary.

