#### 5.5.1 **Primary Efficacy Analysis**

The King's Parkinson's Disease Pain Scale (KPPS) evaluates the burden (global and bedside) and characterises various phenotypes of pain in PD. Its seven domains include 14 items, each item scored by severity (0-3) multiplied by frequency (0-4), resulting in subscores of 0 to 12. The total possible KPPS score (0 to 168) represents the symptomatic burden by pain. The questionnaire will be fill out on Visit 1, Visit 2b, Visit 4, Visit 5 and Visit 6/EDV.

The primary efficacy endpoint of this study is the change from baseline to Visit 6/EDV in the Domain 3 of KPPS. The Domain 3 is about fluctuation-related pain and consists of 3 questions and the total possible Domain 3 score ranges from 0 to 36. The primary efficacy endpoint will be analysed using a two-sided alpha 0.05 using a mixed model for repeated measures (MMRM) assuming the unobserved data is missing at random (MAR) to demonstrate differences in the fluctuation-related pain score between opicapone 50 mg and placebo in addition to current treatment with L-DOPA/DDCI for PD patients with end-of dose motor fluctuations and associated pain.

The following statistical hypotheses will be tested:

$$H_0$$
:  $\mu_T = \mu_C$ 

$$H_1$$
:  $\mu_T \neq \mu_C$ 

where  $\mu_T$  is mean change in Domain 3 of KPPS from baseline in the opicapone treatment arm and  $\mu_C$  is mean change in Domain 3 of KPPS from baseline in the placebo arm. For the rational used under the sample size and hypotheses see section 2.6.

Only subjects without missing baseline score will be used for analysis using MMRM. The MMRM is longitudinal approach which analyse data as collected (including missing values). Analyses will include the fixed, categorical effects of treatment, visit, and treatment-by-visit interaction, as well as the

I-DM-011SAP Page 24 of 49

continuous, fixed covariates of baseline score. The two-sided test estimated results with alpha level of 0.05 will be provided.

An unstructured variance structure will be used to model the within-patient errors. If this analysis fails to converge, the following structures will be tested in order defined below until model convergence is reached:

- Heterogeneous Toeplitz
- Heterogeneous autoregressive
- Toeplitz
- Autoregressive
- Compound symmetry
- Variance components

The Kenward-Roger approximation will be used to estimate degrees of freedom.

Following SAS code will be used to fit MMRM model:

```
PROC MIXED DATA = <DATASET>;

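### Does the drop-out rate below 15% fail to support the SAP's statement that early termination has no impact?

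*SAP*

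**What the plan says.** The protocol synopsis (Sample size) plans on a difference of 3.0 points in KPPS Domain 3, an SD of 5.8, two-sided 0.05 and 80% power, which gives 2 x 60 = 120 evaluable patients. It continues: "A drop-out rate of 15% is assumed, therefore 140 patients need to be randomised". SAP Section 2.6 repeats this and calls the drop-out rate approximate.

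The post-BDRM note in the same SAP section reports 144 screened and 127 randomised, with the shortfall due to early termination. It then says: "As the drop-out rate was less than 15%, the early termination will not have an impact". The next sentence reads: "A total of 120 evaluable patients were required and 122 subjects belong to the full analysis set".

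Four other places bear on what the 122 means:

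- SAP Section 3.1 admits to the full analysis set (FAS) randomised patients "who had at least one post-baseline assessment of primary efficacy measurement". A Visit 6 value is not required.
- The protocol synopsis (Statistical methods) makes the FAS the primary analysis population. Its design section fixes the time point: "The primary analysis will be performed on the data collected at V6".
- SAP Sections 4.10 and 5.5.1 analyse the endpoint with an MMRM under missing at random, so patients with a baseline score and some post-baseline visits contribute.
- SAP Section 4.8 uses early discontinuation visit (EDV) data for efficacy "only if EDV assessments were performed no later than 3 days after last IP intake", and then assigns the visit to the nearest scheduled one.

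**The concern.** A drop-out allowance converts a randomised number into an evaluable number, so it protects the target only at the size for which it was set. Here that size was 140. The note applies the same 15% to 127 and concludes that nothing is lost. As an inference this fails: a drop-out rate of 10% or 14% would satisfy the stated condition and still leave fewer than 120 patients.

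The second sentence also invites a question. The sample size text treats *evaluable* as randomised minus drop-outs. The FAS is a wider group, because a patient who leaves after Visit 4 is a drop-out but still a member. If *evaluable* meant having a Visit 6 value, 122 in the FAS would not by itself show that 120 was reached.

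At stake would be a signed SAP recording as fact that a trial 13 patients short of plan kept its power, when the reason given does not establish it.

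**Working it through.** **Inputs.** Difference 3.0, SD 5.8, alpha 0.05 two-sided, power 80%, 1:1 allocation, drop-out 15%, 140 planned, 127 randomised and 122 in the FAS (all SAP Section 2.6).

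**The plan's own figures.** By the normal approximation, n per arm = 2 x (1.960 + 0.842)^2 x 5.8^2 / 3.0^2 = 58.7, so 59 per arm or 118. With the t-test, n per arm is 59.65, so 60 per arm or 120, as stated. For drop-out, 120 / 0.85 = 141.2 and 140 x 0.85 = 119. So 140 is a fair rounding for an approximate 15%, and the plan's own yield is 119.

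**The 15% rule at 127.**

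- 127 x 0.85 = 107.95, about 108.
- To keep 120: 127 - 120 = 7 losses, 7/127 = 5.5%.
- To keep 119: 127 - 119 = 8 losses, 8/127 = 6.3%.
- From 9 losses (7.1%) to 19 losses (14.96%) the rate is still below 15%, but 118 down to 108 remain.

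The first sentence of the note therefore does not establish its conclusion.

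**The second sentence.** 127 - 122 = 5 patients outside the FAS, 5/127 = 3.9%. On the FAS count, 122 exceeds 120. On a strict Visit 6 count, 120 is met only if at most 122 - 120 = 2 FAS members lack a value, and 119 only if at most 3 do.

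**Power by count.** Two-sample t-test, noncentrality = (3.0/5.8) x sqrt(N/4), with no gain from partial data or baseline adjustment:

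| N counted | Noncentrality | Power |
|---|---|---|
| 108 | 2.69 | 75.9% |
| 118 | 2.81 | 79.6% |
| 119 | 2.82 | 79.9% |
| 120 | 2.83 | 80.2% |
| 122 | 2.86 | 80.9% |

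The extreme case the 15% wording tolerates is 79.9 - 75.9 = 4.0 points below the plan's own 119, and 80.2 - 75.9 = 4.3 points below 120.

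**Why 108 is not the analysis sample.** Suppose 19 patients did drop out. Only 5 randomised patients are outside the FAS, so at least 19 - 5 = 14 of the 19 are in it with post-baseline Domain 3 data. Given a baseline score, the MMRM uses them. If their EDV meets the 3-day rule and falls on days 128 to 200 (SAP Table 4), they even supply a Visit 6 value. The baseline covariate helps as well. If 5.8 is an unadjusted SD of change and baseline correlates 0.31 with change (both assumptions), the residual SD is 5.8 x sqrt(1 - 0.31^2) = 5.51, and 108 patients alone give 80.0%.

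**The case for a change.** The case for rewording is a fair one. The sentence is current SAP text, it is offered as the reason why stopping 13 short does not matter, and as logic it does not hold. *Evaluable* is not defined in the text available, and neither the drop-out count nor the number with a Visit 6 value is given. An MMRM does not turn a patient last seen at Visit 4 into a full Visit 6 observation, so counting all 122 is the favourable end. Correcting the sentence would need only pooled, blinded counts.

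What stands is the narrow point: the 15% clause is a poor reason, and the statement would be better rested on the FAS count alone.

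The rest does not carry. The note does tell the reader which count is set against 120, because the 122 in the FAS appears in the same sentence as the 120. That comparator is natural for a trial whose primary population is the FAS and whose primary model accepts incomplete follow-up. The 108-to-118 range is what the 15% wording would permit, not what any document reports. Only the protocol synopsis and schedule are available here, so the full protocol may define the term. The counts a careful reader would want are largely planned already: withdrawals (Table 15.1.4), attendance by visit (Table 15.1.6), and KPPS by visit with numbers present and missing (the KPPS summary tables, with the default statistics of SAP Section 4.1).

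**Conclusion.** No change to the plan is needed. One explanatory sentence gives a weak reason for a conclusion that the next sentence supports: 122 patients in the primary analysis population against 120 required, or 80.9% power under the planning assumptions.

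That figure takes the difference of 3.0 and SD of 5.8 as given and counts every FAS member as a full observation. Missing Visit 6 values would lower it somewhat, and the baseline covariate would raise it. The outer bound is about 4 points of power, reached only if 19 patients dropped out and neither their partial data nor the baseline adjustment added anything. The true loss may be zero.

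Recruitment is over, so a restated power would guide no decision. The precision achieved will be visible in the confidence interval for the Visit 6 difference. Rewording the note would leave the model, the analysis sets, the hypothesis and the outputs exactly as they are.

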## 2.7 Blinding

Opicapone and placebo capsules will be identical in size, colour, taste and appearance. The packaging and labelling will not allow for any distinction between test and reference drug.

No person involved in conducting the study may have access to the randomisation code before the blind is officially broken.

Unblinding will not be done unless an actual emergency occurs, and knowledge of the patient's allocated treatment arm affects his/her medical treatment. If possible, before breaking the blind the principal investigator or an authorised delegate consults with the SCOPE 24/7 medical contact to ascertain the necessity of breaking the code. The result of unblinding should be kept confidential and will not be recorded in the eCRF.

I-DM-011SAP Page 12 of 49

